3.3 Study Period

Recruitment period: 24 months. Follow-up time points: 6th, 12th, 24th, and 60th months after enrollment.

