3.7 Primary Endpoint

Incidence of major adverse cardiovascular and cerebrovascular events (MACCE) within 24 months after randomization, including all-cause death, recurrent myocardial infarction, stroke, hospitalization for heart failure, outpatient or emergency visits due to worsening heart failure, and repeat revascularization driven by angina pectoris.

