3.12 Statistical Methods

| Primary Endpoint | Statistical Methods | Analysis Time Point |
|--|---|--|
| Incidence of major adverse cardiovascular events (MACE, including cardiac death, non-fatal MI, non-fatal stroke, readmission for heart failure, etc.) within 24 months after randomization | Survival analysis, Kaplan-Meier survival curve, Log-rank test | 24th month after randomization |
| Secondary Endpoints | Statistical Methods | Analysis Time Point |
| All-cause death at 24 and 60 months after randomization | Survival analysis, Kaplan-Meier survival curve, Log-rank test | 24th and 60th months after randomization |
| Recurrent myocardial infarction at 24 and 60 months after randomization | Survival analysis, Kaplan-Meier survival curve, Log-rank test | 24th and 60th months after randomization |
| Stroke at 24 and 60 months after randomization | Survival analysis, Kaplan-Meier survival curve, Log-rank test | 24th and 60th months after randomization |
| Hospitalization for heart failure or outpatient/emergency visits due to worsening heart | Survival analysis, Kaplan-Meier survival curve, Log-rank test | 24th and 60th months after randomization |

| | | |
|--|---|--|
| failure at 24 and 60 months after randomization | | |
| Repeat revascularization driven by angina pectoris at 24 and 60 months after randomization | Survival analysis, Kaplan-Meier survival curve, Log-rank test | 24th and 60th months after randomization |
| Difference in left ventricular ejection fraction (LVEF%) measured by echocardiography compared to baseline after randomization | T-test, Wilcoxon rank-sum test | 24th month after randomization |
| Difference in left ventricular end-systolic diameter/body surface area% measured by echocardiography compared to baseline after randomization | T-test, Wilcoxon rank-sum test | 24th month after randomization |
| Difference in left ventricular end-diastolic diameter/body surface area% measured by echocardiography compared to baseline after randomization | T-test, Wilcoxon rank-sum test | 24th month after randomization |
| NYHA functional classification at 12 and 24 months after randomization | Wilcoxon rank-sum test, Chi-square test | 24th month after randomization |
| KCCQ score at 12 and 24 months after randomization | T-test, Wilcoxon rank-sum test | 24th month after randomization |
| Incidence of drug-related adverse events | Chi-square test | 1st, 3rd, 6th, 12th, and 24th months after randomization |

4. Sample Size Calculation

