This study adopts a 1:1 sample size ratio between the experimental group and the control group, with a one-sided α value set at 0.025 and a power (1- β) of 0.8. Based on preliminary study results and relevant clinical data (referring to PARADISE-MI, EMPACT-MI, COLCOT,

FLAVOUR series studies), event rate estimation will be performed using Kaplan-Meier survival analysis. Assuming an event rate of 16.5% in the control group and 13.2% in the experimental group, the expected enrollment period is 2 years. The sample size will be calculated using PASS software. Considering a 10% dropout rate, 1402 patients will need to be enrolled in each group, totaling 2804 patients.

5. Data Management and Confidentiality

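### Section 4 gives no time horizon for 16.5% vs 13.2% and no follow-up time; read as 24-month rates, 2,804 patients give about 65-69% power for the 24-month endpoint, not 80%

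*Protocol*

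**What the plan says.** Section 4 sets the error rates, "with a one-sided α value set at 0.025 and a power (1- β) of 0.8", and 1:1 allocation. It gives the effect and the accrual time in one sentence: "Assuming an event rate of 16.5% in the control group and 13.2% in the experimental group, the expected enrollment period is 2 years". It then gives the result: "Considering a 10% dropout rate, 1402 patients will need to be enrolled in each group, totaling 2804 patients". The text says that the rates rest on preliminary results and outside trials and that PASS was used. It attaches no time point to the rates and gives no follow-up time or total study duration.

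Section 3.7 defines the primary endpoint as "Incidence of major adverse cardiovascular and cerebrovascular events (MACCE) within 24 months after randomization". The table in Section 3.12 gives the primary analysis as "within 24 months after randomization | Survival analysis, Kaplan-Meier survival curve, Log-rank test | 24th month after randomization". Section 3.3 confirms the accrual time ("Recruitment period: 24 months") and lists visits up to month 60.

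**The concern.** The power of a log-rank test depends on the number of events, which in turn depends on the period the assumed rates cover and on how long each patient is observed. Section 4 gives neither. Sections 3.7 and 3.12 do fix the observation window: no patient contributes more than 24 months to the primary analysis, however early they enrol. The only period the protocol attaches to the primary endpoint is 24 months, so the natural reading of 16.5% and 13.2% is as 24-month cumulative risks. On that reading the stated sample size and the stated power do not fit together.

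What is at stake is the chance of missing the effect the trial was designed to find. The protocol puts it at 20%. With a 24-month window and 24-month rates it is about 31-35%.

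**Working it through.** **Inputs.** From Section 4: one-sided alpha 0.025 (z = 1.960), power 0.80 (z = 0.842), rates 0.165 and 0.132, 1:1 allocation, 10% dropout, 1,402 per arm (1,402 × 0.9 ≈ 1,262 evaluable), 2 years' accrual. From Sections 3.7 and 3.12: 24-month window, log-rank test. Assumptions: exponential survival, and rates taken as 24-month risks unless stated otherwise.

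**Effect and events needed.**
- HR = ln(1 − 0.132) / ln(1 − 0.165) = 0.785; |ln HR| = 0.242.
- Schoenfeld: 4 × (1.960 + 0.842)² / (ln HR)² = 536 events.
- Freedman: (1.960 + 0.842)² × [(1 + HR)/(1 − HR)]² = 541 events.

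**Can 1,402 be reproduced?** With 24-month rates and a 24-month cut it cannot. One patient in each arm yields 0.165 + 0.132 = 0.297 expected events, so:
- Schoenfeld: 536.1 / 0.297 = 1,805 per arm; / 0.9 = 2,006.
- Freedman: 541.3 / 0.297 = 1,823 per arm; / 0.9 = 2,025.
- Two proportions: 1,822 per arm; / 0.9 = 2,024.
- Gradual (exponential) loss reaching 10% by month 24, in place of division by 0.9: 1,899 per arm.

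Even with no loss at all, the requirement (1,805) exceeds 1,402.

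Three sets of inputs do come close to 1,402 after division by 0.9 (Schoenfeld to Freedman):

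| Inputs | Per arm | Difficulty |
|---|---|---|
| 24-month rates, 24 months' accrual, then 24 months' further follow-up, all events to month 48 counted (risks 23.6% vs 19.1%) | 1,396-1,410 | Common close not stated; counts events after month 24 |
| 24-month rates, fixed 36 months per patient | 1,391-1,404 | Not stated; counts events after month 24 |
| 16-month rates, 24-month cut | 1,391-1,404 | No 16-month horizon in the protocol |

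The first uses the accrual time the protocol does give, so it is a plausible source of the figure. If so, the calculation was made for a longer event window than the endpoint allows.

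**Power of the planned size, 24-month rates and 24-month cut.** Power = Φ(√events / 2 × 0.242 − 1.960).

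| Loss | Patients per arm | Events | Power | Simulated (5,000 runs) |
|---|---|---|---|---|
| 10% contribute nothing | 1,262 | 1,262 × 0.297 = 375 | 64.9% | 64.8% |
| 10% lost gradually by month 24 | 1,402 | 396 | 67.3% | 67.9% |
| None | 1,402 | 1,402 × 0.297 = 416 | 69.5% | 69.0% |

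**Sensitivity to the unstated horizon.** For rates read as h-month risks, the 24-month risk is 1 − (1 − p)^(24/h). With a 24-month cut and 1,262 evaluable per arm:

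| Horizon h (months) | Events | Power |
|---|---|---|
| 12 | 693 | 89% |
| 16 | 541 | 80% |
| 18 | 487 | 76% |
| 20 | 443 | 72% |
| 24 | 375 | 65% |

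**What 1,262 evaluable per arm can detect with 80% power in 24 months.** At HR 0.785, it needs 24-month risks of about 23.5% vs 19.0%. With the control risk held at 16.5%, it needs about 12.6% in the experimental group (HR about 0.75).

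**The case against.** The strongest reply is that only the omission is certain and the power loss is conditional. The protocol attaches no horizon to the rates, 24 months included, and the outside studies they come from may have used shorter ones. With 12-month rates the power would be 89%; with 18-month rates it would be 76%, or about 80% if nobody is lost. This stands, and it is why the 65-69% is given as conditional and the fix starts with stating the horizon. It does not rescue Section 4: no shorter horizon appears anywhere, and with 10% loss a horizon of about 16 months or less is needed to reach 80%.

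A second reply is that 1,402 is no slip of arithmetic, because it agrees within about 0.6% with a log-rank calculation using the stated 2-year accrual plus 2 further years. That is fair as a description of where the figure may come from. But the further follow-up is not stated, and the calculation counts events up to 48 months after randomization for the earliest patients, which Sections 3.7 and 3.12 exclude. The fault would then be a mismatch between the sample-size model and the endpoint, with the same effect on power.

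A third point is that 65% and 69% are bounds. The log-rank test uses time before censoring, so dropouts contribute something, and some dropout is expected. Gradual loss, at 67-68%, is the better single estimate. Finally, the accrual time is already stated, so the main gaps are the horizon and the follow-up.

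**Conclusion.** The concern holds. It is certain that Section 4 omits the horizon of the rates and the follow-up time, and that its 80% power cannot be reproduced from its stated inputs with the 24-month endpoint. On the natural reading (24-month risks, exponential survival, events counted to month 24), 1,402 per arm gives about 65-69% power, with about 67-68% most realistic. It yields roughly 375-416 events where 536-541 are needed. This size of shortfall rests on the 24-month reading, which the sponsor must confirm; a shorter horizon would reduce it or remove it. The point must be fixed, because the power claimed for the primary endpoint has no support in the protocol as written.

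**What to change.** Amend Section 4 to state the horizon of 16.5% and 13.2%, and the accrual time, follow-up time and formula entered in PASS. Recompute with each patient's follow-up cut at 24 months.

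- If the rates are 24-month risks, restate that 2,804 patients give about 65-69% power for 16.5% vs 13.2%, or 80% power for about 16.5% vs 12.6% (HR about 0.75, 1,262 evaluable per arm).
- If they have another horizon, state it, give the implied 24-month risks and report the power for those.

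The cost is one paragraph in a protocol amendment and, on the 24-month reading, a less favourable power statement. Correcting the figure needs no change in enrolment. It is for the sponsor to decide whether to accept the restated power, re-size, or prospectively redefine the primary analysis. Re-sizing to 80% would mean about 4,010-4,050 patients in total, about 1,200 more than the planned 2,804.

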5.1 Data Management

Study data will be retained for at least 3 years after the completion of study outcomes (including relevant papers, research reports, etc.). Unauthorized processing of study data without patient authorization or research institution approval is prohibited. If study data is stored electronically, it is recommended to back up the data to optical discs regularly, especially for important data which requires multiple backups. Relevant software should be used to ensure timely data storage, and special attention should be paid to the security of electronic data storage.

The review committee or ethics committee will conduct regular audits or inspections of data security. Its main responsibility is to systematically and independently verify all study-related processes and documents to determine whether the implementation of the study process, the accuracy of data recording, analysis, and reporting comply with the study protocol, good clinical practice (GCP), International Council for Harmonisation (ICH) guidelines, and any regulatory requirements.

5.2 Data Confidentiality

Throughout the study, the health information of all patients must be kept confidential, and unauthorized access to data is prohibited. Each patient will be assigned a unique identification number, and patient data will be stored in locked cabinets at the clinical center with data encryption to restrict data access. Relevant regulations on the confidentiality of patient information should be roughly informed to patients in the informed consent form. In accordance with relevant regulations on the protection of patient health information, relevant health personnel are entitled to access study data.

6. Informed Consent

This study intends to recruit patients with acute ST-segment elevation myocardial infarction. To protect vulnerable populations, pregnant women, minor patients, patients with mental illness or cognitive impairment, and staff and students of the research center will be excluded.

Prior to collecting study data, the following details of the study must be informed to patients: 1. This is a Phase IV clinical study; 2. Patient participation is strictly voluntary, and no compensation is required for withdrawing from the study; 3. Patients can withdraw from the study at any time; 4. Potential risks and benefits are disclosed; 5. Necessary communication and contact will be maintained.

Participants will have sufficient time to understand the study and ask questions before

participating. They will be informed of the study purpose, available treatments, randomization assignment, the need to cooperate with outpatient follow-up and complete some auxiliary examinations. The patient's decision to accept or refuse to participate in the study will not affect clinical diagnosis and treatment.

All patients or their legal representatives must sign the informed consent form after fully understanding the study before conducting any study-related activities and treatments. Those who do not sign the informed consent form are not eligible to participate in the study. A copy of the signed informed consent form will be made, with the original retained in the patient's medical record and the copy provided to the patient or their legal representative for safekeeping. All study-related data must be supported by medical records, cardiovascular angiography images, blood test results, ECG, echocardiography, and cardiac magnetic resonance results. The acquisition of these data is mainly to support routine medical care and basic research.

7. Reporting and Management of Adverse Events

7.1 Reporting of Adverse Events

All adverse events: Timely measures should be taken for management, and events should be recorded in the case report form (CRF).

Serious adverse events (SAE): Timely measures should be taken for management, and events should be recorded in the CRF. The investigator will decide whether to discontinue or reduce the drug dosage. The ethics committee, drug clinical trial institution, and sponsor should be immediately notified, and the national and provincial drug regulatory authorities should be reported within 24 hours. SAEs must be reported through the "Hospital Intranet Adverse Event and Near-Miss Non-Punitive Reporting System". Specific procedures: see the figure below.

[figure not shown])

- No emergency treatment required
- Emergency treatment required, immediate reporting
- Report within 24 hours
- Hospital Medical Affairs Department: [name]
- Note: For night-time reports, please call the general duty room: [name]
- Responsible for proper handling
- State Drug Administration Safety Supervision Department Pharmaceutical Research Supervision Office: [name]
- Provincial Food and Drug Administration Registration Office: [name]
- Ethics Committee: [name]

- Sponsor/CRO
- Report to the Adverse Event and Near-Miss Non-Punitive Reporting System via the hospital intranet
- Conduct follow-up and summarize handling opinions
- Report to the hospital leadership in charge)

7.2 Management of Adverse Events

1. Cardiac adverse reactions (including tachycardia, palpitations): Complete laboratory biochemical examinations, ECG, echocardiography, etc. If necessary, perform cardiac electrophysiological examinations to clarify the cause. For patients with severe symptoms, discontinue fexofenadine hydrochloride and administer antiarrhythmic drugs if necessary.
2. Nervous system reactions (including headache, somnolence, dizziness, etc.): Consult a neurologist for auxiliary diagnosis, complete neurological physical examinations and imaging examinations to rule out emergency conditions such as intracranial hemorrhage and infection. Administer analgesic drugs and physical therapy if necessary.
3. Psychiatric reactions (including sleep disorders, anxiety, etc.): Consult a psychiatrist for auxiliary diagnosis, complete relevant scales to assess the patient's emotional and sleep status. Administer hypnotic drugs or anti-anxiety medications if necessary.
4. Gastrointestinal reactions (including diarrhea, nausea, etc.): Consult a gastroenterologist for auxiliary diagnosis, supplement body fluids via oral or intravenous infusion, and administer antidiarrheal, antiemetic, and other symptomatic drugs if necessary.
5. Immune-related skin reactions (including rash, urticaria, pruritus, etc.): Consult a dermatologist for auxiliary diagnosis. Perform histopathological examination if diagnosis is difficult. Apply topical moisturizers or hormonal ointments locally. For patients with severe skin lesions, administer oral/intravenous hormones and immunosuppressive therapy.

Management of serious adverse events:

Severe allergic/hypersensitivity reactions (including angioedema, chest tightness, dyspnea, flushing, other systemic immediate allergic reactions, etc.): During the treatment of severe allergic reactions, close monitoring of cardiac function, blood pressure, respiration, and blood oxygen saturation should be performed. If severe dyspnea occurs due to laryngeal edema or bronchospasm, tracheal intubation or tracheotomy should be considered, and cricothyrotomy may be performed in emergency situations. For patients with grade II or above severe allergic reactions, epinephrine intramuscular injection is the first choice, administered at a dose of 0.01 mg/kg body weight, with a maximum single dose not exceeding 0.5 mg, at a concentration of 1 mg/ml (1:1000). If the effect is unsatisfactory after 5-15 minutes, repeat the administration. For patients with grade IV reactions who have experienced or are about to experience cardiac or respiratory arrest, epinephrine should be administered intravenously at a single dose of 0.5-1 mg, at a concentration of 0.1 mg/ml (1:10000). For patients with grade III reactions who have established venous access and are under monitoring, epinephrine can be administered intravenously at a single dose of 0.1-0.2 mg, at a concentration of 0.1 mg/ml (1:10000). If the effect is unsatisfactory after 3-5 minutes, repeat the administration. H1

receptor antagonists, β 2 receptor agonists, and glucocorticoids can be used as second-line medications. Fluid resuscitation can be used for patients with severe allergic reactions accompanied by circulatory instability, with a usual fluid volume of 20 ml/kg, adjusted according to the patient's condition. After the patient is rescued from danger, monitoring should be continued for at least 12 hours, including monitoring of heart rate, rhythm, blood pressure, respiration, blood oxygen saturation, and urine output.

8. Protection Measures for Vulnerable Populations

Patients with acute MI are critically ill and clinically considered a vulnerable population. This study will take all necessary measures to fully protect the privacy rights, right to life and health, right to informed consent, and other rights and interests of vulnerable participants.

8.1 Right to Privacy

High attention should be paid to and protection provided for the privacy of vulnerable participants. Investigators will assume confidentiality responsibilities, using de-identified data instead of the participants' personal information to ensure the anonymity of participants. In addition, during the recruitment and informed consent process, investigators are obligated to inform patients of the study's confidentiality system, and participants can only participate in the trial after understanding and agreeing.

8.2 Right to Life and Health

The right to life and health of vulnerable participants should be protected as the most important and fundamental right. The drugs used in this study are all marketed drugs, and their safety has been confirmed in previous clinical trials. The dosage and administration are in accordance with drug instructions and clinical practice. In addition, participants will receive regular follow-up during the study period, and adverse events will be promptly managed and reported. The clinical event committee will assess whether participants can continue to participate in the trial. Furthermore, during the informed consent process, the risks, benefits, and compensation for damages associated with participating in the trial will be fully informed to participants, who can only participate after understanding and accepting them.

8.3 Right to Informed Consent

Informed consent is a prerequisite for vulnerable participants to participate in clinical trials. Investigators will fully inform participants of the study content, risks, benefits, rights protection, compensation for damages, etc., and answer participants' questions. Participants must sign the informed consent form after fully understanding the study before participating. For participants who lack the capacity for independent decision-making, verbal consent should be obtained from the participants themselves, and their legal representatives should sign the informed consent form.

9. References

1. Lindstrom, M. et al. Global Burden of Cardiovascular Diseases and Risks Collaboration,

1990-2021. *Journal of the American College of Cardiology* 80, 2372-2425, doi:10.1016/j.jacc.2022.11.001 (2022).

2. Zhang, Q. et al. Signaling pathways and targeted therapy for myocardial infarction. *Signal transduction and targeted therapy* 7, 78, doi:10.1038/s41392-022-00925-z (2022).
5. Zhao, M. et al. Targeting fibrosis, mechanisms and clinical trials. *Signal transduction and targeted therapy* 7, 206, doi:10.1038/s41392-022-01070-3 (2022).
6. Wynn, T. A. & Ramalingam, T. R. Mechanisms of fibrosis: therapeutic translation for fibrotic disease. *Nature medicine* 18, 1028-1040, doi:10.1038/nm.2807 (2012).
7. King, T. E., Jr. et al. A phase 3 trial of pirfenidone in patients with idiopathic pulmonary fibrosis. *The New England journal of medicine* 370, 2083-2092, doi:10.1056/NEJMoa1402582 (2014).
8. Richeldi, L. et al. Efficacy and safety of nintedanib in idiopathic pulmonary fibrosis. *The New England journal of medicine* 370, 2071-2082, doi:10.1056/NEJMoa1402584 (2014).
9. Ni, C. et al. Flavin Containing Monooxygenase 2 Prevents Cardiac Fibrosis via CYP2J3-SMURF2 Axis. *Circulation research*, 101161circresaha122320538, doi:10.1161/circresaha.122.320538 (2022).
